8.2.5 Pharmacokinetic Analysis

No overall PK analysis is planned in this study. However, serum samples will be collected at Week 0/Day 0 (pre-dose); at Weeks 2, 4, 8, 12, 16, 20, 24, 32, 40, 48 and at the Follow-up or ET visit 56 days (8 weeks) after the last dose of study drug. These samples will be stored and may be used to evaluate serum adalimumab levels in conjunction with assessment of AEs, loss of response, or compliance or to correlate with ADA assay results. The PK data will be summarized descriptively for any subject for whom these samples were assayed. These samples will not be used to assess biomarkers genetic markers. These serum samples will be destroyed 2 years after the completion of the study (database lock).

8.3 Determination of Sample Size

Approximately 500 subjects will be randomized and treated for this trial (approximately 250 per arm in Treatment Period 1).

The sample size was determined to show comparable efficacy for the following endpoint based upon the PASI at Week 12:

- The percentages of subjects in each group, CHS-1420 and Humira, achieving PASI-75 at Week 12

For the proportion of subjects achieving a PASI-75, it has been assumed that 70% of subjects will be responders in both the reference group, Humira, and the CHS-1420 group. The sample size will produce 90% power to establish equivalence at the 5% alpha level (2-sided) with an equivalence margin of 15% (absolute). Subjects who lack a PASI assessment at Week 12 will be considered non-responders in the primary analyses.

The margin for equivalence has been based statistically on the study results from Menter (2008) and to a lesser extent Gordon (2006). At 12 weeks, Menter had PASI-75 responses of 68% (554/814) for Humira and 5% (20/398) for control. This results in a treatment effect of approximately 63% (absolute). A lower 95% confidence bound (2-sided) for the difference in response rates can be calculated to be 59%. The proposed 15% margin for demonstrating equivalence is much smaller than the demonstrated benefit associated with Humira.

Though Gordon (2006) was a considerably smaller study, at 12 weeks this study had similar PASI-75 responses of 71% (70/99) for Humira and 19% (9/48) for control. This results in a treatment effect of approximately 52% (absolute). Pooling Gordon and Menter using the method of Der Simonian and Laird, yields a lower bound on the treatment effect of at least 50% which also supports the use of a 15% equivalence margin.

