3.2 Rationale for Study Design/Dose Level

No clinical trials to evaluate the efficacy and safety of CHS-1420 in subjects with PsO have been performed to date. The design of this study is based on 2 clinical studies comparing adalimumab 80 mg ×1 followed by 40 mg QOW to placebo in subjects with moderate to severe psoriasis ([Menter, et al., 2008](#)), ([Gordon, et al., 2006](#)).

In a 52-week, randomized, double-blind, placebo-controlled, multicenter study, 1212 subjects with moderate or severe psoriasis were randomized 2:1 to receive either adalimumab or placebo at an initial dose of 80 mg followed by 40 mg QOW for the first 15 weeks ([Menter, et al., 2008](#)). Main exclusion criteria included exposure to anti-TNF therapy, other skin disease or infection that could interfere with evaluation, allergy to adalimumab or its constituents, current oral or injectable corticosteroid use, untreated tuberculosis (TB), poorly controlled medical conditions, history of neurologic symptoms suggestive of central nervous system demyelinating disease, and history of cancer or lymphoproliferative disease (other than successfully treated nonmelanoma skin cancer or localized carcinoma in situ of the cervix). Subjects achieving a PASI-75 response at Week 16 were eligible to continue in an open-label study and receive adalimumab 40 mg QOW for Weeks 17 through 31. Subjects who maintained a PASI-75 response at Week 33 were re-randomized to adalimumab or placebo QOW for an additional 19 weeks. The primary efficacy endpoints for this study were percentages of subjects achieving PASI-75 response at Week 16 relative to baseline and percentages of subjects losing adequate response after Week 33. At Week 16, 580/814 (71%) of adalimumab-treated versus 26/398 (7%) of placebo-treated subjects achieved at least PASI-75 scores. PASI-75 results at 12 weeks were also reported with 68% of subjects on Humira and 5% of subjects on placebo achieving PASI-75. The mean % change in PASI at 12 weeks for Humira was 76 compared to 15 for placebo. From Week 33 to Week 52, 5% of adalimumab-treated and 28% of placebo-treated subjects lost adequate responses.

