In a 12-week, double-blind, placebo-controlled, multicenter study, 147 subjects with moderate to severe psoriasis were randomized to receive either an initial dose of 80 mg adalimumab followed by 40 mg adalimumab QOW, every week, or placebo ([Gordon, et al., 2006](#)). Subjects who completed the initial 12-week trial were eligible to continue in a 48-week extension trial. The primary efficacy analysis was the percentages of subjects achieving at least PASI-75 relative to baseline at Week 12 (for the initial trial) and at Week 24 (for the extension trial).

At 12 weeks, 53% of subjects receiving adalimumab QOW and 80% of subjects receiving adalimumab every week achieved PASI-75 compared to 4% of subjects receiving placebo (P<0.001).

Menter (Menter, et al., 2008) and Gordon (Gordon, et al., 2006) used the PASI-75 as the primary outcome measure with the PASI-75 evaluated at 16 weeks and 12 weeks, respectively. Both studies reported mean % change in PASI at Week 12: 76% Humira vs. 15% Placebo and 70% Humira vs. 14% placebo for Menter, 2008 and Gordon, 2006, respectively.

In this study (CHS-1420-02), eligible subjects are those who have a diagnosis of chronic PsO for at least 6 months that is moderate to severe as defined by a PASI score of greater than or equal to 12, Physician's Static Global Assessment (PSGA) score of greater than or equal to 3 (based on a scale of 0 to 5), and body surface area (BSA) affected by chronic PsO of greater than or equal to 10%. Subjects will be stratified by BMI < 30 kg/m² or ≥ 30 kg/m² and age < 65 years or ≥ 65 years (Menter, 2010).

The proposed dose level and dose regimen are consistent with that in the Humira (EU) Summary of Product Characteristics (AbbVie EU, 2014) and the Humira package insert (AbbVie US, 2014). In this study, 2 SC injections (2 pre-filled syringes, [80 mg]) of study drug will be administered on Week 0/Day 0. From Week 1/Day 7 through up to Week 23/Day 161, 1 SC injection (1 pre-filled syringe [40 mg]) of study drug will be administered QOW.

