4.3 Method of Assigning Subjects to Treatment Groups

Once the subject has signed the ICF at Screening, site personnel will assign a subject identification number (ID). The subject ID will include the site number (3 digits), and 3 digit subject number, assigned sequentially starting with 001. This number will be utilized to identify the subject throughout the study period. Once the subject ID has been assigned, the site will contact the Interactive Voice Response System/Interactive Web-based Response System (IXRS) to register the subject ID. Dropouts (subjects who discontinue study treatment early, and subjects who are randomized but not treated) will not be replaced. No individual is allowed to re-enter the study if previously randomized and dosed.

Subjects will be assigned to study drug in accordance with the randomization schedule generated using permuted block randomization by an independent statistician.

Approximately 500 subjects will be randomly assigned in a 1:1 ratio (approximately 250/arm) to receive 1 of the following treatments in Treatment Period 1:

- 2 SC injections (2 pre-filled syringes, [80 mg]) of Humira on Week 0/Day 0 and 1 SC injection (1 pre-filled syringe [40 mg]) of Humira QOW from Week 1/Day 7 through up to Week 15/Day 105.
- 2 SC injections (2 pre-filled syringes, [80 mg]) of CHS-1420 on Week 0/Day 0 and 1 SC injection (1 pre-filled syringe [40 mg]) of CHS-1420 QOW from Week 1/Day 7 through up to Week 15/Day 105.

Subject randomization will be stratified by body mass index (BMI) (less than ($<$) 30 kg/m² or greater than or equal to (\geq) 30 kg/m²), age (<65 yrs or ≥ 65 yrs) and region.

At the end of Treatment Period 1 (Week 16), subjects taking Humira will either begin dosing with CHS-1420 or continue with Humira during Treatment Period 2. A single randomization will be used to determine treatment in Treatment Periods 1 and 2. In effect, a 2:1:1 randomization will be used where for each 2 subjects randomized to receive CHS-1420 an additional 2 will be assigned to receive Humira in Treatment Period 1. For the subjects assigned to Humira in Treatment Period 1, 1/2 of these will be randomly assigned to continue with Humira for Treatment Period 2 and 1/2 will be assigned to switch to CHS-1420 for Treatment Period 2.

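### Do the conflicting Week 12 placebo rates for the 147-subject study (4% in Section 3.2, 19% in Section 8.3) undermine the 15% equivalence margin?

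*Combined protocol and SAP*

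**What the plan says.** Section 3.2 (Rationale for Study Design/Dose Level) describes two historical placebo-controlled studies of adalimumab.

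- Smaller study: "147 subjects with moderate to severe psoriasis were randomized to receive either" adalimumab every other week (QOW), adalimumab every week, or placebo. At Week 12, "53% of subjects receiving adalimumab QOW and 80% of subjects receiving adalimumab every week achieved PASI-75 compared to 4% of subjects receiving placebo". Arm sizes are not given.
- Larger study (1212 subjects, QOW after the initial dose): "PASI-75 results at 12 weeks were also reported with 68% of subjects on Humira and 5% of subjects on placebo achieving PASI-75".

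Section 8.3 (Determination of Sample Size) returns to both studies. "The margin for equivalence has been based statistically on the study results from" the larger study and, to a lesser extent, the smaller one.

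- Larger study: "PASI-75 responses of 68% (554/814) for Humira and 5% (20/398) for control", with a lower 95% bound of 59% for the difference.
- Smaller study: "at 12 weeks this study had similar PASI-75 responses of 71% (70/99) for Humira and 19% (9/48) for control", an effect of about 52 points.
- DerSimonian-Laird pooling of the two "yields a lower bound on the treatment effect of at least 50% which also supports the use of a 15% equivalence margin".

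This trial doses every other week only. Section 4.3 specifies, for the reference arm, "1 SC injection (1 pre-filled syringe [40 mg]) of Humira QOW from Week 1/Day 7 through up to Week 15/Day 105".

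**The concern.** One study, one endpoint and one visit carry two placebo rates, 4% and 19%. The active figures also differ in form. Section 3.2 reports two regimens separately, whereas Section 8.3 reports a single Humira group of 99. Since 99 + 48 = 147, the full study size, that group may merge the QOW and every-week arms, and Section 8.3 does not say so.

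The equivalence margin decides the primary conclusion, so its historical basis should be traceable. If the smaller study's effect were wrong or came partly from a regimen not used here, the pooled bound could be overstated and the 15% margin could look better supported than it is.

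**Working it through.** **1. Can the two placebo rates be reconciled?** For 9 responders to round to 4%, 9/n must lie in [3.5%, 4.5%), which gives n = 201 to 257. The study randomized 147. In any arm of 147 or fewer, at most 6 responders round to 4%; in an arm of 48, only 2 do. So at least one section is wrong, and the documents do not show which.

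**2. Does merging explain the active count?** Search every split of 99 into an arm rounding to 53% and an arm rounding to 80%. The totals run from 54 to 75, and 70 arises once: 18/34 + 52/65. Near-equal arms (26/49 + 40/50) give 66. Merging is possible but remains an inference.

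**3. The plan's own figures.** For each study d = p1 − p2 and v = p1(1−p1)/n1 + p2(1−p2)/n2.

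| Study | Rates | d | SE = √v | Lower 95% bound |
|---|---|---|---|---|
| Larger | 554/814 = 0.681; 20/398 = 0.050 | 0.630 | 0.0197 | 0.630 − 1.96 × 0.0197 = 0.592 |
| Smaller (8.3) | 70/99 = 0.707; 9/48 = 0.1875 | 0.520 | 0.0726 | 0.377 |

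The stated 59% and the 52-point effect both reproduce.

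DerSimonian-Laird pooling, with w = 1/v:

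- Weights 2584.1 and 189.9; fixed-effect mean 0.623; Q = 2.17.
- τ² = (Q − 1)/(Σw − Σw²/Σw) = 1.170/353.8 = 0.0033.
- Random-effects mean 0.597, SE 0.0508; lower 95% bound 0.597 − 1.96 × 0.0508 = 0.497.

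The 90% interval gives 0.513. A pooled variance within each study gives 0.515 at 95%. The stated 50% therefore holds to rounding.

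**4. Section 3.2's rates in place of Section 8.3's.** Arm sizes are assumptions, because the documents do not give them.

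| Smaller-study input | Pooled lower 95% bound | Bound ÷ 15% |
|---|---|---|
| Section 8.3 as written (70/99 against 9/48) | 49.7% | 3.3 |
| Control alone changed to 2/48 | 59.8% | 4.0 |
| Both active arms, 62 to 71 of 99, against 2/48 | 58.9% to 59.9% | 3.9 to 4.0 |
| QOW against placebo, 53% against 4%; QOW arm 33 to 66, placebo arm 48 to 52, whole counts | 43.3% to 46.3% | 2.9 to 3.1 |
| Larger study alone, no pooling | 59.2% | 3.9 |

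In the least favorable case the margin is 15/43.3 = 35% of the lower bound. On the larger study alone it is 15/59.2 = 25%.

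**5. Does the trial's size depend on any of this?** With 70% in both arms, n = 2 × 0.7 × 0.3 × (1.96 + 1.645)²/0.15² = 242.6, so 243 per arm. At 250 per arm, SE = √(0.42/250) = 0.0410 and power = 2Φ(0.15/0.0410 − 1.96) − 1 = 91.1%, consistent with the stated 90%. No rate from the smaller study enters.

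**The case for a change.** The best case for acting is that the contradiction is genuine. Both statements are complete sentences of current text, and neither rounding nor a change of denominator reconciles them. Section 8.3 reports a pooled bound built on one of the two versions. On Section 3.2's rates for the regimen this trial actually uses, that bound falls to about 43% to 46%, below the stated 50%. The word used to compare the two studies also fits poorly: their control rates in Section 8.3 are 18.75% and 5.0%, 13.7 points apart. Checking the source and correcting a line would cost little.

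The factual core of this stands: one of the placebo rates is wrong, and the make-up of the 99 is unstated. The consequence does not follow. The bound can be reproduced from the counts printed beside it; only the correctness of an input is in doubt. The regimen point loses most of its force because the larger study, which carries the argument, used QOW dosing after the initial dose and agrees across both sections. The comparison wording is editorial: the Humira rates it also covers, 71% and 68%, are close.

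**Conclusion.** A clerical inconsistency in cited background, with nothing to gain from changing the plan. The placebo rates of 4% and 19% are incompatible, and a sponsor who next revises the document may wish to check them against the source. But the margin rests mainly on the larger study, whose 59.2% bound is nearly four times 15%. Every version of the pooled bound, from about 43% to 60%, is roughly three to four times the margin. The margin, the 250 per arm, the power and the primary confidence-interval rule stay the same whichever figure is right.

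This rests on two assumptions: that the larger study's counts are correct, as their agreement across Sections 3.2 and 8.3 suggests, and that the unstated arm sizes lie in the ranges used above. It concerns only whether this discrepancy disturbs the 15% margin; whether 15% is clinically acceptable is a separate question.

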9 DATA MONITORING COMMITTEE

An independent data monitoring committee (DMC) will be convened under a separate charter to review accumulating data and monitor the safety of subjects over the course of the study. In addition to periodic reviews of the accumulating safety data, after the last subject completes the evaluations at the Week 12 visit (or a an earlier time if adequate Week 12 data are available), the DMC may review the unblinded database for safety and efficacy as well as whether or not equivalence is likely to be shown. The sponsor will remain blinded to individual subject treatment assignments and will be informed only of the group level results for public announcement. The DMC will not be requested to close the trial early for equivalence, only to recommend if the study is unlikely to achieve its objective. As such, no statistical adjustment is proposed.

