	
injection technique before administering study drug and on an electronic diary (eDiary), to track compliance and subject-reported ISRs. Subjects/caregivers will contact the eDiary following each injection to document dosing on the day of injection and any possible ISRs after the injection. During site visits, subject questionnaires will be completed by subjects using an electronic diary in the clinic.
 
The primary efficacy endpoint is the proportion of subjects achieving 75% improvement in Psoriasis Area and Severity Index (PASI-75) at week 12. The proportion of subjects achieving PASI-75 at 16 weeks will be a secondary efficacy endpoint.
 
An independent, unblinded Data Monitoring Committee will review Treatment Period 1 study data to determine if there is adequate safety and efficacy to warrant continuing the study to completion.
 
Subjects who discontinue study drug for any reason during Treatment Period 1 will be encouraged to return for all study visits through Week 16 if applicable and for the ET visit 56 days (8 weeks) after the last dose of study drug per the protocol Schedule of Procedures. Subjects who discontinue study drug for any reason during Treatment Period 2 or 3 will be encouraged to return for the Follow-up or ET visit 56 days (8 weeks) after the last dose of study drug (also per the protocol Schedule of Procedures). The Follow-up or ET visit will include evaluation of safety and immunogenicity (formation of anti-drug antibodies [ADAs]).

Study Centers	Approximately 160 active clinical sites worldwide will participate in this clinical trial.
Sample Size	The sample size determination is based on demonstrating a comparable PASI-75 at Week 12. Assuming that 70% of subjects in both the reference group, Humira, and the CHS-1420 group achieve PASI-75, with a statistical margin of 15% (absolute), approximately 250 subjects per treatment group will produce 90% power to establish equivalence at the 5% alpha level (2-sided) for the period 1 comparison. Subjects who lack follow-up data for the week 12 assessment will be considered non-responders in the primary analyses.
Study Population	Adult male and female subjects with moderate to severe chronic PsO.

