The first dose of study drug on Week 0/Day 0 will be self-administered or administered by a caregiver at the investigative site, and subjects will be monitored for adverse reactions and ISRs during the 2 hours after this dose. Subsequent doses will be self-administered or administered by a caregiver at home. Subjects/caregivers will be trained on injection techniques and the electronic diary (eDiary) used to track compliance and subject-reported ISRs. Subjects/caregivers will contact the eDiary following each injection to document dosing on the day of injection and any possible ISRs after the injection.

The primary efficacy endpoint is the proportion of subjects achieving 75% improvement in Psoriasis Area and Severity Index (PASI-75) at Week 12. When an adequate amount of data are available for the primary endpoint, an independent, unblinded Data Monitoring Committee (DMC) will review the accumulating safety and efficacy to determine if the data are adequate to warrant continuing the study.

Subjects who discontinue study drug for any reason during Treatment Period 1 will be encouraged to return for all study visits through Week 16 and for the ET visit 56 days (8 weeks) after the last dose per the protocol Schedule of Procedures, and subjects who discontinue study drug for any reason during Treatment Period 2 or 3 will be encouraged to return for a Follow-up or ET visit 56 days (8 weeks) after the last dose of study drug (also per the protocol Schedule of Procedures). This Follow-up or ET visit will include evaluation of safety and immunogenicity (formation of anti-drug antibodies [ADAs]).

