8.1.4 Per Protocol Population

The Per Protocol Population is defined as those subjects in the FAP completing at least 12 weeks of treatment and follow-up with respect to the PASI and have no protocol violations that may affect the interpretation of the primary efficacy endpoint. These violations will be identified by the Sponsor prior to study unblinding.

Subjects will be allocated to the treatment arm they are randomized to for a particular Treatment Period of analysis.

8.1.5 Open Label Extension Population:

The Open Label Extension Population is defined as those subjects receiving at least 1 dose of open label treatment. Subjects will be allocated to the treatment arm they received in Treatment Period 2.

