10.5 Data Validation

Validation checks programmed within the eCRF system, as well as supplemental validation performed via review of the downloaded data, will be applied to the data in order to ensure accurate, consistent, and reliable data. Data identified as erroneous, or data that are missing, will be referred to the investigative site for resolution through data queries.

Once all data have been monitored, queried, cleaned, and considered ready for final database lock, the Investigator will electronically sign the eCRF for each subject at the completion of the study.

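### Section 9 does not confine the release of group-level results to complete, locked Week 12 data

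*Combined protocol and SAP*

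**What the plan says.** Section 9 sets up the committee under its own charter: "An independent data monitoring committee (DMC) will be convened under a separate charter to review accumulating data". Its efficacy review is placed after the last subject's Week 12 evaluations, with an alternative: "or a an earlier time if adequate Week 12 data are available), the DMC may review the unblinded database for safety and efficacy". The review also covers whether equivalence is likely to be shown. The next sentence deals with what leaves the committee: "The sponsor will remain blinded to individual subject treatment assignments and will be informed only of the group level results for public announcement". The committee is not asked to stop the trial for equivalence, "only to recommend if the study is unlikely to achieve its objective", and on that ground the section makes no statistical adjustment.

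Two other places describe the same review differently. Section 3.1 triggers it with "When an adequate amount of data are available for the primary endpoint". The synopsis (Study Design) says "An independent, unblinded Data Monitoring Committee will review Treatment Period 1 study data to determine if there is adequate safety and efficacy", and Treatment Period 1 runs to Week 16.

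The only lock described is the final one, in Section 10.5: "Once all data have been monitored, queried, cleaned, and considered ready for final database lock". On Per Protocol exclusions, Section 8.1.4 and the synopsis say "These violations will be identified by the Sponsor prior to study unblinding", without defining that unblinding. Section 4.6 keeps the study double-blind through Treatment Periods 1 and 2.

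**The concern.** The primary endpoint, PASI-75 at Week 12, comes from a clinician's rating (Section 6.1.1.1). If a comparative result became public while some subjects had yet to reach Week 12, their assessors could know it when they rated. The sponsor could also know it while Week 12 queries were being resolved. The usual protection is that only a recommendation leaves the committee until the primary data are complete and locked. Section 9 does not say this, and it provides for group-level results to be announced.

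The section also sits uneasily with its own rationale. A committee whose efficacy role is limited to advising that the trial is unlikely to succeed needs to send out only that advice. At stake is the credibility of the primary comparison, not its nominal error rate.

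**Working it through.** **1. The plan's own figure.** Inputs from Sections 8.2.2 and 8.3: 250 per arm, 70% response in both arms, margin 15 points, 95% two-sided interval.
- SE = sqrt(2 × 0.7 × 0.3 / 250) = 0.0410.
- Power = 2Φ(0.15/0.0410 − 1.96) − 1 = 0.911.

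This reproduces the stated 90%. Nothing in this point changes it.

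**2. What the text requires before release.**
- *Timing of the review:* after the last Week 12 visit or earlier (Section 9). The earlier option rests on a sufficiency of data that neither Section 9 nor Section 3.1 quantifies.
- *What is reviewed:* unblinded safety and efficacy, including the prospect of equivalence (Section 9).
- *What the sponsor receives:* group-level results for public announcement (Section 9). The sentence names no date and does not itself say efficacy; that reading comes from the sentence before it.
- *State of the data at release:* no requirement that Week 12 data be complete, cleaned or locked. Section 10.5 describes only the final lock.
- *Per Protocol list:* fixed before study unblinding (Section 8.1.4). Section 9 keeps the sponsor blinded to individual assignments after release, so a group-level release need not count as that unblinding.

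Together these permit an early release. They do not state that one is planned.

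**3. How many primary assessments could be open.** The documents give no minimum completeness, so the fraction t of Week 12 data in hand is an assumption, shown over a range. With about 500 subjects (Section 8.3), open assessments = 500 × (1 − t):
- t = 0.9: 50
- t = 0.7: 150
- t = 0.5: 250
- release after the last Week 12 visit (t = 1): 0

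In the last case only Week 12 data cleaning and, on one reading, the Per Protocol list remain open.

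**4. What cannot be sized.** These counts measure exposure, not bias. A published result of similar response could draw the remaining ratings in both arms toward one expectation, which would favour equivalence. A published result suggesting a difference would not act that way. The documents contain nothing from which either effect could be estimated.

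**5. What remains after any fix.** For the last subject, the blinded visits at Weeks 16, 20 and 24 follow Week 12, up to 24 − 12 = 12 weeks. A public group result would overlap with them. They supply secondary endpoints, and Section 8.2.2 presents efficacy data from Treatment Period 2 by treatment sequence.

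**The case against.** The strongest reply is that early public release is inferred. The default timing is after the last Week 12 visit, the earlier option is a parenthesis, and the review itself is optional. The announcement sentence gives no timing. An early look that yields only a recommendation, with an announcement after the last Week 12 visit, is at least as natural a reading. The charter may say exactly that. This largely stands: what is shown is a permission in the protocol text, not a declared plan. It does not remove the point, because the protocol provides for both the early look and the release and places no condition between them.

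A second reply is that the mechanism is speculative. Assessors already know that two active products are being compared, under a protocol that assumes the same response in both arms. What an announcement would add is unknown. This also stands, so no size or direction is claimed.

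A reader might go further in three ways that the documents do not support.
- *Type I error is inflated.* Under the stated use the committee cannot stop for equivalence and can only advise that success is unlikely. That gives no extra chance of declaring equivalence.
- *The Per Protocol population is compromised.* Violations must already be identified before study unblinding, the Full Analysis Population is primary (Section 8.1.2), and Section 8.2.2 assigns no analysis to the Per Protocol population. Only a clarification is warranted.
- *The gap between an early and a final estimate measures the harm.* That gap is ordinary sampling variation and would arise with perfectly unbiased ratings.

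Safeguards also exist: matched syringes (Section 4.6), continued blinding to individual assignments (Section 9) and an audit trail for data changes (Section 10.1). They limit the risk, but none of them controls when a group result becomes known.

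**Conclusion.** The point holds as a gap in release control. As written, Section 9 can be read to let the sponsor and sites learn a comparative result before all primary assessments are made and Week 12 data are cleaned. The exposure ranges from no open primary assessments, if release follows the last Week 12 visit, to 250 of about 500 at an assumed 50% completeness. The resulting bias cannot be sized or signed from the documents. Sample size, power and alpha are unaffected.

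The conclusion rests on two readings: that the group-level results include efficacy, as the context indicates, and that no rule outside the supplied text restricts release. The charter could overturn the second. A reader might infer that the sponsor intends to publish interim efficacy; the text does not say so. This is a worthwhile, inexpensive correction and not a defect that invalidates the design.

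**What to change.** - **Sections 9 and 3.1:** state that any efficacy review before the last subject's Week 12 visit returns only the DMC's recommendation on continuing. State that group-level results are released only after the last Week 12 visit and a Week 12 data lock.
- **Synopsis (Study Design):** align the description of the DMC review with Section 9.
- **Section 8.1.4 and synopsis (minor clarification):** state that Per Protocol violations are identified before any group-level efficacy result is released to the sponsor.
- **DMC charter:** carry the same release rule if it is not already there.

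The cost is wording, one additional data lock and a later announcement. The change does not protect the blinded Week 16 to 24 visits from a public group result; Section 9 should acknowledge that as a remaining limitation.
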